**Intended Use of Test Article**

The [REDACTED] Regular, Super, and Super Plus absorbency tampons are over the counter medical devices intended to be inserted into the vagina by menstruating females for the absorption of menstrual fluid, after which is removed and discarded. The population of individuals that will use these devices are menstruating females of any age. In the United States, tampons are Class II medical devices per 21 CFR 884.5470 (Unscented Menstrual Tampons).

**Description of Test Article**

The [REDACTED] tampon is a [REDACTED] tampon in an applicator. The applicator aids in insertion of the tampon device into the vagina during menstruation and is removed after deployment. The removal of the tampon involves an attached [REDACTED] string which extends externally for ease of access.

The [REDACTED] device consists of a tampon (absorbent core, overwrap cover and withdrawal string) in a three-piece applicator individually wrapped in a printed plastic film. The tampon is composed

of a [REDACTED] absorbent core, a [REDACTED] overwrap cover that surrounds the [REDACTED] core, and a white or pink rayon/polyester string [REDACTED]  
[REDACTED] to enable tampon removal. [REDACTED]  
[REDACTED]

The three-piece applicator consists of an outer insertion tube, referred to as the barrel, which has a textured grip and closed rounded tip in a petal-like design at the distal end (end of the applicator closest to the cervix during tampon insertion). The applicator also includes a short inner tube, referred to as a plunger, which snaps into place with a short middle telescopic tube to form an elongated plunger of the proper length to expel the tampon from the applicator barrel into the vagina. The applicator barrel holds the tampon prior to use, and the withdrawal string of the tampon is threaded through the telescope/plunger tube and a portion remains outside the applicator prior to use. [REDACTED]  
[REDACTED]  
[REDACTED]

The final tampon product was subjected to extensive biocompatibility testing per FDA guidance and current ISO 10993 biocompatibility testing guidance for class II medical devices with additional assessments for tampons. [REDACTED]  
[REDACTED]  
[REDACTED]  
[REDACTED]  
[REDACTED]

This study will include two absorbencies of [REDACTED] tampon: regular and super. [REDACTED]  
[REDACTED] tampons have been marketed in the United States for more than 10 years. The composition of the modified tampon is the same as described above, but with an adjusted placement of the withdrawal string.

#### **Concomitant Medications**

Medication use within 30 days of Visit 1 and throughout the duration of the subject's participation will be recorded.

#### **Randomization**

Subjects will be assigned a unique subject identification number by the site at screening. Following completion of the screening procedures, eligible subjects will be assigned to either the regular or super absorbency arm, based on the tampon absorbency the subject uses most often. Within each arm, the order in which the test and reference tampons will be used will be randomized.

A randomization schedule that was created by the unblinded biostatistician at [REDACTED] will be provided to each site. Unique subject randomization numbers will be assigned by the site according to the site specific randomization schedule. Randomization numbers should be assigned sequentially within each arm.

#### **Exam Procedures**

A subset of 60 subjects in each arm will undergo a gynecological examination at each visit. Gynecological exams may also be conducted as needed for any subject to assess adverse events.

The following will be included in the exam:

- Symptom assessment

Prior to the vaginal exam, subjects will be asked to complete a short questionnaire regarding vaginal symptoms they may be experiencing. The purpose of this assessment is to alert the clinician of any possible conditions that may need to be addressed for the health of the subject and that may affect eligibility.

- Visual assessment

This gynecological exam will consist of a visual inspection of the perineum, vulva, urethra, vagina, and cervix. Use of a clear speculum and light are expected for this exam. Each anatomical location will be evaluated for lesions. Each lesion will be characterized according to one of the following types:

Type	Epithelium	Blood Vessel	Description	Coverage	Comment
A	Intact	Intact	 Erythema  Edema	 ≤ 50%  > 50%	Provide specific location and any other relevant findings
B	Intact	Disrupted	 Petechia  Ecchymoses	 ≤ 50%  > 50%	
C	 Disrupted, superficial  Disrupted, deep	 Intact  Disrupted	 Peeling  Abrasion  Ulceration  Laceration	 ≤ 50%  > 50%	
D	N/A	N/A	 Other	 ≤ 50%  > 50%	Provide description of the lesion, specific location, and any other relevant findings

Type D lesions can be other lesions not related to epithelial or blood vessel disruption such as cysts, polyps, neoplasms, etc.

Subjects with presence of any Types B or C lesions at baseline will be excluded from the study. Subjects with a Type A lesion (erythema or edema) may be included as long as the coverage area is ≤ 50%. Subjects with Type D lesions will be excluded at the discretion of the investigator.

Superficial epithelial disruption does not penetrate into the subepithelial tissue. Deep epithelial disruption penetrates into and exposes the subepithelial tissue and possibly blood vessels. If bleeding from the finding is present, the disruption should be recorded as deep.

Lesions identified after the screening visit will be considered adverse events. Severity is determined by disruption of the epithelium and blood vessels. Lesions with an intact epithelium and intact blood vessels are considered mild (Types A). Any lesion that has a deep disruption in the epithelium is considered severe (Type C with deep epithelial disruption). All others are considered moderate (Type B and Type C with superficial epithelial disruption). Severity of “Other” (Type D) lesions will be determined by the Investigator.

- Vaginal discharge

The quantity, odor, color, and consistency of the vaginal discharge will be assessed during the vaginal exam by the investigator to determine whether a vaginal infection is suspected.

- Vaginal pH

Vaginal pH measurements should be taken using pH testing strips and instructions provided. The testing strips measure pH in increments of 0.5, with a minimum range of 4.5 – 7.5.

- Suspected infection

A subject who has symptoms of a vaginal infection or urinary tract infection at screening is not eligible to participate in the study. If a subject develops a vaginal infection or UTI during the study, she will stop using the study product and switch to menstrual pads.

The subject may be treated by the investigator or referred for treatment at the discretion of the investigator. Subjects may continue using study product after treatment is complete and symptoms have resolved, if appropriate for the study design. Development of vaginal infections after screening are recorded and analyzed as adverse events.

- Other abnormal findings

Any other abnormal findings during the vaginal examination will be recorded. Subjects may be excluded for abnormal findings. Abnormal findings recorded after the screening visit will be recorded and analyzed as adverse events.

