#### **Visit 2 – Post-Use Visit**

For all subjects, Visit 2 will include the following:

- Test article collection (used and unused products)
- Diary review
- Test Article dispensation (if not in the Subset Population)
- Diary dispensation (if not in the Subset Population)
- Diary re-training, if needed
- Tampon integrity assessment
- Adverse event collection

For all subjects in Subset Population, Visit 2 will also include the following:

- Gynecological symptom assessment
- Gynecological exam (visual inspection, infection assessment, vaginal discharge, and vaginal pH)

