3.5. Method of Assigning Subjects to Treatment Groups

Subjects will be assigned a unique subject identification number by the site at screening. Following completion of screening procedures, eligible subjects will be assigned to either the regular or super absorbency arm, based on the tampon absorbency the subject uses most often. Within each arm, the order in which the test and reference tampons will be used will be randomized.

A randomization schedule that was created by a biostatistician at [REDACTED] will be provided to each site. Blinding was not required as this is an open-label study. Unique subject randomization numbers will be assigned by the site according to the site-specific randomization schedule. Randomization numbers should be assigned sequentially within each arm.

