3.6. Blinding and Unblinding

Not applicable as this is an open-label study.

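### Neither document limits the examiner's knowledge of which tampon was used, although the examiner's judgements feed a tolerability criterion that has no threshold

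*Protocol*

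**What the plan says.** **Masking.** SAP 3.6 (Blinding and Unblinding) reads in full: "Not applicable as this is an open-label study". SAP 3.5 adds: "Blinding was not required as this is an open-label study". Neither section considers the examiner separately from the user.

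**Who is examined, and for what.** Protocol 8, Exam Procedures: "A subset of 60 subjects in each arm will undergo a gynecological examination at each visit", and "Each anatomical location will be evaluated for lesions". Findings are sorted into Types A to D and a coverage category. The investigator also assesses discharge to decide whether infection is suspected.

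**What becomes of a finding.** In the same section: "Lesions identified after the screening visit will be considered adverse events". For grading, "Severity is determined by disruption of the epithelium and blood vessels", while severity of Type D lesions is left to the investigator. Under Protocol 12, Recording Adverse Events, the investigator rates the relationship of each event to the test article.

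**How the data are used.** In Protocol 11, Validation Criteria (repeated in SAP 2.1.1), tolerability must be judged acceptable on review of the results, and no limit is given. SAP 8.4 bases that judgement on exam findings and adverse events.

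**Access to product identity.** Protocol 8, Randomization: "Unique subject randomization numbers will be assigned by the site according to the site specific randomization schedule". Protocol 9 states which code letters mean test and which mean reference, and puts the code on every box and every returned bag.

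**The concern.** Open-label use by the woman does not require an examiner who knows the product. Whether faint erythema is recorded, how a lesion is typed, whether discharge suggests infection, and whether a finding is attributed to the tampon can all be influenced, without intent, by knowing whether the new or the marketed design was used.

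The crossover does not protect against this. Comparing each woman with herself removes differences between women, but an assessment tendency tied to the product remains in the within-woman comparison.

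At stake is the tolerability criterion. With no threshold, the reviewers rely on the recorded findings and on the test and reference columns printed side by side in SAP Tables 14.3.6.1.1 and 14.3.6.1.2. The adverse event tables show the same split, by product period.

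**Working it through.** The plan gives no figure on this point. Its sample size rests on elongation and is unaffected. The check therefore sets the passages side by side.

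**1. Routes by which the examiner can learn the product**
- The order schedule is held and applied at the site (Protocol 8, Randomization).
- Coded boxes are dispensed at Visit 1 and, for the exam subset, at Visit 3 (Protocol 10).
- Each returned clear bag and the red bag carry the code (Protocol 9, Test Article Dispensation, Collection, and Management).
- The codes are decoded in Protocol 9, Test Article(s).
- The woman handles labelled boxes and bags and may mention the code.
- With two products in two cycles, a code learned at Visit 2 reveals the product assessed at Visit 4.

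No passage closes any of these routes for the examiner.

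**2. What is judgement and what is rule**
- *Rule or instrument:* severity of Types A to C once the lesion is typed; the definition of superficial and deep disruption, with bleeding counted as deep; pH read from strips.
- *Judgement:* whether a lesion is seen and recorded, its type, coverage by eye, suspected infection, Type D severity, and relationship to the product.

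The severity rule narrows the discretion but does not remove it. Because severity follows from type, a shift in typing passes directly into the severity of the adverse event.

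**3. Order of procedures**
- *Visits 2 and 4 (Protocol 10):* tasks for all subjects come first, including product collection and diary review. The exam follows under tasks for the Subset Population. This groups tasks by population and sets no sequence.
- *Table 1 (Protocol 2 and SAP 3.7):* the exam is listed above product collection and diary review. This is also not stated to be a sequence.
- *Visit 3:* the exam is listed before dispensation.
- *Visit 1:* assignment follows completion of screening procedures (Protocol 8, Randomization), so the baseline exam precedes knowledge of the order.

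The gap is thus mainly at Visits 2 and 4, where the order is unspecified. Visit 3 also matters: a finding there is an adverse event, and if its onset precedes first use of the second product, SAP 9.1 assigns it to the first product's period.

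**4. Scale**
- Exam subset: 2 × 60 = 120 of 738 women, or 120/738 = 16.3%. The other 738 − 120 = 618 have no scheduled exam.
- If one, two or three women per arm (assumed counts) had a lesion unrecorded with one product only, that product's any-lesion rate would fall by 1/60 = 1.7, 2/60 = 3.3 or 3/60 = 5.0 percentage points. This shows how sensitive the table is; it does not estimate bias.
- Only non-recording lowers the any-lesion row. A lesion given a lower type still counts there and only moves between the type rows.

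**The case against.** The strongest reply is that open-label conduct was declared, exam findings are summarised descriptively with no test between products, and Type A to C severity follows a fixed rule. All of that stands and keeps the point small. None of it concerns the examiner's knowledge of the product when findings are detected, typed and attributed.

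A second reply is that relationship depends on timing of use, and insertion and removal times are diary data. That is fair, but dates of use can be obtained without the code.

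Stronger readings are tempting, and the documents do not support them:
- *That the plan places the exam after product hand-in.* The visit lists set no order, and Table 1 lists the exam first.
- *That examining before hand-in would mask the examiner.* It closes one route. The schedule, dispensing, the woman herself and the inference from Visit 2 remain.
- *That masking needs no extra staff.* Neither document describes site staffing.
- *That the boxes conceal identity because they show only code letters.* They also carry the study number, absorbency level, quantity, manufacturer and an investigational-device caution, and the protocol decodes the letters.
- *That the results will favour one product.* Nothing in the documents gives a direction.

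**Conclusion.** The point holds in a limited form. The plan leaves the examiner free to know the product while making judgements that feed a tolerability criterion without a threshold, and it sets no order of procedures that would reduce that exposure. It affects scheduled exams in 120 women and the adverse events detected at them. It does not affect the elongation endpoint, the sample size, power or alpha.

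The direction and size of any bias cannot be estimated from the documents. The conclusion assumes only that some lesion and attribution calls are discretionary, which the exam form and the relationship scale show. This is a worthwhile refinement and gives no reason to doubt the design as a whole.

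**What to change.** Amend Protocol 8 (Exam Procedures) and Protocol 10 as follows:

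- **Visits 2 and 4:** the gynecological exam is completed and recorded before returned bags, unused tampons or the diary are opened.
- **Visit 3:** the exam precedes dispensation, as already listed.
- **Exam form:** carries no tampon code.
- **Examiner:** does not consult the randomization schedule or dispensing log. Where existing staffing allows, someone else does the dispensing, collection and diary review.
- **Women in the subset:** are asked not to name the product to the examiner.
- **Relationship, for exam-detected findings only:** recorded before the code is looked up, where safety allows, using dates of use taken without the code.

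SAP 3.6 could then note that the user is unmasked while the examiner's knowledge of the product is limited as far as practicable.

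**Cost.** Protocol and site-manual wording and a check of the exam form; no added visits. Separating roles depends on site staffing and is therefore conditional.

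**Limits.** Masking is reduced in risk, not guaranteed: the site holds the schedule, a code learned at Visit 2 reveals the second product, and one person may both dispense and examine. Adverse events found in the returned diary (Protocol 12, Collection and Reporting of Commercial Product Complaints) and those in the 618 women outside the subset are not covered. The report should say so.

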### **Tampon Assessment Procedures**

Each used tampon will be collected within a clear plastic sealable bag and frozen until returned to the study site. Tampons will be collected by study staff, removed from the bag, and photographed using standardized photography set-up. Study staff will measure elongation of each used tampon using a provided calibrated ruler. If elongation occurs, measurements will be taken to the nearest mm from the base of the tampon to the furthest point of the absorbent material protruding from the base. If no elongation occurs, a value of 0 mm will be recorded. Any measurement >10 mm will be considered elongation.

## **9 TEST ARTICLE AND MANAGEMENT**

### **Test Article(s)**

- Modified [REDACTED] Tampons (test tampons)
  - Regular Absorbency – Code Letter: BR
  - Super Absorbency – Code Letter: BS
- Commercial [REDACTED] Tampons (reference tampons)
  - Regular Absorbency – Code Letter: CR
  - Super Absorbency – Code Letter: CS

### **Test Article Packaging and Labeling**

All test articles will be packaged in boxes resembling commercial [REDACTED] tampon packaging. Each box will contain 16 tampons and a commercial product insert containing general tampon usage instructions, as well as applicable safety information. Each box will minimally contain the following information:

- study number
- applicable test article code letters (BR, BS, CR, or CS)
- absorbency level
- quantity of the contents
- the name and place of business of the manufacturer
- the statement, "CAUTION - Investigational device. Limited by Federal (or United States) law to investigational use."

### **Test Article Accountability**

With each shipment of test articles, investigative sites will receive a copy of the study material packing listing the details of the contents of the shipment. Investigative sites should sign and date the enclosed packing list and verify receipt of the shipment. The original signed packing list should be retained in the site's regulatory document repository. Packing lists will be reviewed, and any items received by the site, including their lot numbers and code letters, will be documented in the accountability log. Copies of the accountability log will be monitored for completeness and accuracy.

### **Test Article Dispensation, Collection, and Management**

The following items will be dispensed to the subject at the visit prior to product use:

- 1 box of tampons according to the randomization schedule
- 1 used tampon collection kit containing the following:
  - 16 small clear sealable individual used tampon collection bags
  - 1 medium sized red sealable bag to collect all individually sealed tampon bags
- 1 diary containing study instructions and diary entry forms for each tampon used
- 1 cooler bag (dispense 1 per subject for the entire study)
- 1 freezer pack
- 1 large opaque white drawstring bag used to return the cooler bag containing the red tampon collection bag, completed diary, and any unused tampons to the site

Subjects will collect each used tampon and place it in a clear bag, labeled with the following information:

- Study Number
- Subject Number
- Menstrual Cycle (1 or 2)
- Tampon Number (e.g., #1, #2, #3, etc.)
- Tampon Code (CR, CS, BR, or BS)

Each of the clear bags containing a used tampon will be placed inside of the single red sealable bag and placed in the freezer until returned to the clinic. The red bag will be labeled with the following information:

- Study Number
- Subject Number
- Menstrual Cycle (1 or 2)

- Tampon Code (CR, CS, BR, or BS)

If a subject is not at home at the time of tampon removal, the subject can place the tampon in the clear collection bag in the cooler bag provided until the subject returns home and can place it in the red bag in the freezer.

Following the last tampon use, subjects will return to the clinic, with the following items in the white drawstring bag provided:

- cooler bag containing the red tampon collection bag with all used tampons
- completed diary
- all unused tampons.

Study staff will document the number of used and unused tampons collected, verify that there is a diary entry for each used tampon, verify the accuracy and completeness of diary entries, and address and document any discrepancies.

## 10 STUDY VISIT SCHEDULE

Subjects will be assigned to one of two arms in the study: a regular absorbency arm or a super absorbency arm. Within each arm, a subset of 60 subjects (Subset Population) will undergo gynecological exams prior to and following tampon use. The study visit schedule is the same for both arms of the study.

For subjects in the Subset Population, the study will consist of 4 visits for each study subject, 2 visits for each menstrual cycle: one before and after each menstrual cycle.

For all other subjects, the study will consist of 3 visits: a screening and pre-use visit, and two post-use visits.

Pre-use visits will be conducted within 72 hours prior to expected menstruation. Post-use visits are to be completed within 72 hours following the last tampon use for that menstrual cycle.

The schedule of visits and timing of procedures are summarized in the Proposed Schedule of Events (Table 1 - Proposed Schedule of Events).

### Visit 1 – Screening/Baseline/Pre-Use Visit

For all subjects, Visit 1 will include the following:

- Signing of informed consent
- Review of inclusion and exclusion criteria
- Collection of demographic information
- Review of medical history
- Review of concomitant medications
- Questionnaire to determine type of tampon used historically
- Randomization
- Test article dispensation
- Diary training

For all subjects in Subset Population, Visit 1 will also include the following:

- Gynecological symptom assessment
- Gynecological exam (visual inspection, infection assessment, vaginal discharge, and vaginal pH)
- Packaging/labeling interview

#### **Visit 2 – Post-Use Visit**

For all subjects, Visit 2 will include the following:

- Test article collection (used and unused products)
- Diary review
- Test Article dispensation (if not in the Subset Population)
- Diary dispensation (if not in the Subset Population)
- Diary re-training, if needed
- Tampon integrity assessment
- Adverse event collection

For all subjects in Subset Population, Visit 2 will also include the following:

- Gynecological symptom assessment
- Gynecological exam (visual inspection, infection assessment, vaginal discharge, and vaginal pH)

